### 3.7 Study protocol /flow chart

### 3.7 Statistical Analysis

Statistical analysis will be performed using the available SPSS software version 19. All numerical data will be subjected to normality testing using Shapiro-Wilk test. All normally distributed data will be expressed as mean  $\pm$  standard deviation (SD) whereas non-normally distributed data were expressed as median (IQR). For normally distributed data, parametric test with Student's t-test will be used. For non-normally distributed data, the Mann-Whitney test will be used or equivalent nonparametric tests. Within groups, the Wilcoxon rank sum test will be used. For qualitative data, Chi-Square test and Fisher's Exact test will be used. The significant p-value will be taken as  $<0.05$  or in the case of multiple comparisons it will be adjusted with a Bonferonni correction.

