### 2.2 Primary Objective:

- To measure the volume of pleural effusion drainage (in mls) 48 hours following randomization

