### 3.6 Recruitment/Data Collection

Subjects with pleural infection (complex parapneumonic effusion or empyema) with poor outflow  $\leq 150$ cc pleural fluid from chest drain over 24 hours of insertion with standard medical therapy who are eligible for this study will be offered to participate into this study. Patient will be informed that this is an 'off label' drugs and a written informed consent will be obtained.

All patients will undergo chest tube/drain insertion. The decision to insert chest drain, the size of chest drain and when to initiate intrapleural t-PA/DNase is determined by the chest physician.

Ultrasound of thorax and chest radiograph will be performed within 24 hours before randomization. Ultrasound of thorax is performed by chest physician with curve probe (ultrasound Mindray, model Z5) for confirmation of complex pleural effusions and chest tube's position. Complex pleural effusion on ultrasound is defined as fibrin strands or septa within the pleural effusion along with presence of loculations in pleural cavity. A baseline chest radiograph will be performed within 24 hours prior to intrapleural fibrinolysis or pleural irrigation to ensure the chest tube position.

Demographic data was collected prior to randomization, which consist of age, gender, ethnicity, BMI, comorbidities. Subjects will be randomized with a block of 4 (using sealed envelope) with random permutations of 2 groups : pleural irrigation group and intrapleural t-PA and DNase.

All patients that prescribed intrapleural t-PA/DNase during the study period will receive a standard dose of medications as below (Appendix 1).

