### Medication Regimen :

t-PA (Alteplase) 5mg and DNase (Pulmozyme)5mg

t-PA (Alteplase) that is available in our pharmacy is 50mg ampoule and DNase (Pulmozyme) is 2.5mg per ampoule

The number of installation of intrapleural t-PA/DNase depends on the discretion of the treating physician (at least 6 hours apart between each dose). 5mg of Alteplase (t-PA) and 5mg DNase are diluted in each 50ml of 0.9% sodium chloride solution. t-PA and DNase are not mixed together in one syringe. The detailed method of t-PA/DNase therapy administration is described in Appendix 1. In brief, both medication are administered sequentially which t-PA is first instilled intrapleurally and the chest tube is then clamped for 45 minutes, then unclamped to allow free drainage for 45 minutes. The same procedure is then repeated for DNase. Selection of the timing of treatment and removal of chest tube are depending on the chest physician's judgement.

However, as for patients who were randomized into pleural irrigation group, subjects were administered 250 ml of 0.9% sodium chloride via chest tube a three way tap from a drip stand which were allowed drainage freely over 1 hour. Pleural irrigation will be performed minimum of 3 installations and maximum of 9 installation (3 times per day).

Both groups received standard care of treatment : which includes regular flushing of chest drain to maintain patency using 20mls of normal saline.

The primary outcome was to evaluate the volume of pleural effusion drainage (in mls) 72 hours following randomization. The volume drained measured after subtracting the amount of volume administered as per protocol.

The secondary outcome are measured by the change in the area of pleural opacity in chest x-ray (day 7 post t-PA/DNase compared to baseline), measured as the percentage of the ipsilateral hemithorax occupied by effusion. The area of pleural opacity and the area of the ipsilateral hemithorax will be measured digitally by two radiologists using Horos Project Software, v3.2.1 as described previously in Multicentre Intrapleural Sepsis Trial 2 (MIST-2)

Other outcomes that will be monitored include :

1. Inflammatory markers including serum C-reactive protein (CRP) & white blood count
2. Length of hospital stay in days
3. The need of surgical intervention within 30 days
4. Adverse effects :
  - a. Chest pain required escalation of analgesics
  - b. Systemic bleeding
  - c. Pleural bleeding

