Net Volume of pleural fluid drained (ml) post IPFT	Baseline	Day 1	Day 2	Day 3
	√	√	√	√
Cumulative pleural fluid drained post IPFT				√

[figure not shown]
Operational Definition:

[figure not shown]
- Treatment success: significant amount of pleural drainage post intervention, reduction of opacity on chest x-ray and resolution of inflammatory markers on day 7 without surgical intervention within 30days
- Treatment failure:
  - Poor drainage from chest drain, failure of resolution of pleural effusion or empyema at least 50% reduction on opacity on chest x-ray and clinical evidence of ongoing infection that requires surgical intervention within 30days post randomization or death before discharge.

All patients will be followed up in respiratory clinic day 30 after discharge or phone call if patient defaulted clinic appointment.

Data will be collected prospectively (Appendix 5) by reviewed patient demographics, clinical data on length of hospital stay, pleural fluid analysis, intrapleural therapy, radiographic characteristics, adverse events, Laboratory data (blood leukocyte count, C-reactive protein, haemoglobin level), Intrapleural therapy data including number of chest tubes, duration of chest tube in pleural cavity and cumulative volume of pleural fluid drained. Besides that, length of hospital stay, treatment outcomes, surgical interventions and the occurrence of complications are recorded.

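### A normality test on the trial's own data sets the primary effect measure, and the planned tests are unadjusted although Day 0 opacity, CRP and WBC are collected in both arms

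*Combined protocol and SAP*

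**What the plan says.** Section 3.7 Statistical Analysis applies one rule to every numerical variable: "All numerical data will be subjected to normality testing using Shapiro-Wilk test". If the data pass, "For normally distributed data, parametric test with" Student's t-test is used and the summary is mean and SD. If they fail, "For non-normally distributed data, the Mann-Whitney test will be used or equivalent nonparametric tests", and the summary changes too: "whereas non-normally distributed data were expressed as median (IQR"). The section does not give the Shapiro-Wilk cut-off, does not say whether the arms are tested separately or together, and does not name the equivalent test.

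No outcome is exempt, so the rule covers the primary outcome. Section 2.2 gives that outcome as "To measure the volume of pleural effusion drainage (in mls) 48 hours following randomization"; under Medication Regimen it reads "The primary outcome was to evaluate the volume of pleural effusion drainage (in mls) 72 hours following randomization", net of the volume instilled. The two time points need reconciling, but the rule applies to either.

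No section names a covariate or a regression model. Baseline data are nevertheless collected. Section 3.6 says "A baseline chest radiograph will be performed within 24 hours prior to intrapleural fibrinolysis or pleural irrigation", and the Monitoring Parameters tables schedule chest X-ray, CRP and full blood count at Day 0 and Day 7 in both arms. The tables headed "Net Volume of pleural fluid drained (ml) post IPFT", and their irrigation counterpart, also have a Baseline column. Section 2.3 defines opacity and WBC/CRP as reduction or change from day 1 (randomization) to day 7.

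**The concern.** A t-test compares mean volumes. A Mann-Whitney test asks whether volumes in one arm tend to be larger than in the other. These can have different answers, and the plan lets the observed data decide which question is put. Hypothesis 1 in section 2.4 (more volume with IPFT) does not settle it. In an open-label trial, a test rule with unstated details also leaves room for choice once results are visible.

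The two arms may well differ in spread as well as location. Under Medication Regimen, irrigation runs from 3 to 9 instillations, the number of t-PA/DNase instillations is at the physician's discretion, and crossover is allowed at any point. That is where the choice between means and ranks matters most.

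Separately, randomisation is in blocks of 4 with no stratification factor stated, and there are about 39 patients per arm. Chance imbalance in baseline severity is possible, and unadjusted tests neither correct it nor use the information in the baseline values.

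**Working it through.** **1. The plan's own figure.** The only size calculation is for failure rates of 0.15 and 0.32 with power 0.8 and a printed type I error of 0.5 (section 3.3). Two-sided, with z = 0.6745 and 0.8416 and mean rate 0.235:

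- n = [0.6745 × √(2 × 0.235 × 0.765) + 0.8416 × √(0.15 × 0.85 + 0.32 × 0.68)]² / 0.17² = (0.404 + 0.494)² / 0.0289 ≈ 28
- Continuity correction: (27.95/4) × [1 + √(1 + 4/(27.95 × 0.17))]² ≈ 38.8, so 39 per arm.

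The figure reproduces, but it concerns a failure rate. The documents give no SD, distribution or power for volume, so the 80% starting power below is an assumption.

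**2. What the pre-test does.** Simulation, 4,000 trials per setting, 39 per arm, Shapiro-Wilk cut-off 0.05 (assumed), arms tested together or separately. The effect is 0.634 SD, from (1.96 + 0.8416) × √(2/39).

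| Assumed shape | Trials sent to Mann-Whitney |
|---|---|
| Normal | 5-10% |
| Lognormal, CV 0.1 | 15-19% |
| Lognormal, CV 0.2 | 41-47% |
| Lognormal, CV 0.3 | 69-78% |
| Lognormal, CV 0.4 | 88-95% |
| Lognormal, CV 0.5 | 96-99% |
| Lognormal, CV 0.75 or more | about 100% |

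- Same distribution in both arms: type I error about 4-6%; power within about 1 point of the better test.
- With the effect present, the t-test and Mann-Whitney disagree on significance in about 6-20% of trials.
- Equal means, unequal shapes: the rule rejects in 15% of trials (normal CV 0.5 v lognormal CV 0.75) and 32% (lognormal CV 0.5 v 1.0), against 5-6% for the t-test.

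The last result has a simple cause. A lognormal median is the mean divided by √(1 + CV²). With equal means, the medians are 1/√1.25 = 0.89 and 1/√2 = 0.71 of that mean. The rank test detects this real difference, but it is not a difference in mean volume.

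**3. Adjusting volume for baseline.** Linear adjustment multiplies the variance by 1 − r², where r is the correlation of baseline with outcome. From 80% power at two-sided 0.05, with near-normal data, power = Φ(2.80/√(1 − r²) − 1.96):

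- r = 0.1: 2.80/0.995 − 1.96 = 0.85, about 80%
- r = 0.3: 2.80/0.954 − 1.96 = 0.98, about 84%
- r = 0.5: 2.80/0.866 − 1.96 = 1.27, about 90%

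**4. Day-7 opacity, CRP and WBC.** The comparator here is a change score. With equal variances at baseline and day 7, its variance is 2(1 − r) of the outcome variance, against 1 − r² when adjusted:

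- r = 0.3: 1.40 v 0.91, a ratio of 0.65
- r = 0.5: 1.00 v 0.75, a ratio of 0.75

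The ratio is (1 + r)/2, which never exceeds 1.

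**5. Does a raw-scale mean model help if volume is skewed?** Simulated power of the existing rule v linear regression on baseline with robust errors (lognormal volumes, multiplicative effect, 39 per arm):

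| CV | r | Existing rule | Raw-scale regression |
|---|---|---|---|
| 0.5 | 0.1 | 77% | 72% |
| 0.5 | 0.5 | 77% | 84% |
| 0.75 | 0.3 | 77% | 73% |
| 1.0 | 0.3 | 77% | 67% |
| 1.0 | 0.5 | 77% | 73% |

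A separate run at CV 1.0, r = 0.3 gave 75% v 65%. A baseline-adjusted rank analysis showed no such loss in the same kind of simulation.

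**The case against.** The strongest defence is that the two-stage rule does little measured harm. That stands when the arms share a distribution. Nor is disagreement between the two tests caused by the pre-test: it would recur between any primary analysis and its sensitivity analysis. What the defence does not answer is that the effect measure remains open, and that the rule answers a different question from the t-test when spreads differ.

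A reader might infer three stronger things.

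- *The choice of test is a toss-up.* That holds only for mild skew, around CV 0.2 in the table. With marked skew the rule almost always lands on Mann-Whitney. The documents give no distribution for volume, so neither case can be asserted.
- *Adjustment gains power for volume at no cost, and precision is known to be lost.* No correlation is given, and at r = 0.1 the gain is negligible. On the raw scale with strong skew and low correlation, the adjusted mean model is worse than the existing rule. The covariate closest to the outcome, drainage before randomisation, is capped at 150 ml by the entry criteria, so its correlation may be small. Baseline opacity has no such cap, but its correlation is equally unknown.
- *Baseline is ignored throughout.* It is not: section 2.3 defines opacity and WBC/CRP as change from baseline. Under the equal-variance model, however, a change score is never more precise than adjustment and can be much less so.

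**Conclusion.** The point holds in limited form. The primary effect measure is not fixed in advance, because a normality test on the trial's own data selects both the test and the summary, and every planned comparison is unadjusted although usable baseline values are collected.

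The harm from the pre-test is small if the arms share a shape. It could be large for a claim about mean volume if they do not: about 32% rejection at equal means in the lognormal CV 0.5 v 1.0 case, which is an assumed scenario and not an estimate for this trial.

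For day-7 opacity, CRP and WBC, the case for adjustment needs no figure from outside the plan: the variance ratio against a change score is (1 + r)/2 under equal variances. It applies to absolute change; if a relative percentage change is meant for opacity, the formula does not carry over exactly. For volume, the gain runs from almost nothing at r = 0.1 to about 10 points of power at r = 0.5, on an assumed 80% start and near-normal data.

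This should be changed before outcome data are analysed. The printed type I error of 0.5 and the 48 v 72 hour conflict are separate and larger problems, which this change does not resolve.

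**What to change.** 1. **Day-7 opacity, CRP and WBC.** Analyse each by linear regression on arm and the outcome's own baseline, reporting the adjusted difference with a 95% CI, in place of unadjusted tests of change. Use the log scale for CRP if it is skewed. State which value is the baseline: section 2.3 says day 1, but chest X-ray and CRP are scheduled at Day 0 and not Day 1, while WBC is scheduled at both.

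2. **Net volume.** Delete the Shapiro-Wilk step. Prespecify one effect measure and one analysis, adjusted for baseline opacity, and name the other approach as a sensitivity analysis. Choose the scale with skew in mind:
   - a mean difference with robust errors, if the mean volume is the quantity of interest and marked skew is not expected;
   - a baseline-adjusted rank analysis, if strong skew is expected.

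   A log scale needs care here, because volume after subtracting the amount instilled can be zero or negative.

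3. **Timing.** Make the choice from clinical expectation or from data outside the trial, before any comparison by arm.

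The cost is analysis-plan wording. No new data are needed, and linear regression and ranking can be run in the SPSS software already named. The trade-off is in the scale: a raw-scale mean model gives up power under strong skew and low correlation, and a rank analysis does not give a difference in millilitres.

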### 2.3 Secondary Objectives:

- To determine the reduction of pleural opacity (in percentage) on chest radiograph from day 1 (randomization) to day 7
- To determine the change on inflammatory markers (WBC/CRP) from day 1 (randomization) to day 7
- To determine the outcome :
  - Length of hospital stay (in days) after randomization for each group
  - The need of surgical intervention in 30 days
  - Adverse effects following t-PA/DNase and pleural irrigation
  - Mortality rate at 30 days

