## **OBSERVATION AFTER ADMINISTRATION OF t-PA (ALTEPLASE) & DNase (PULMOZYME)**

1. Observe the patient for:
  - a. deterioration in clinical condition
  - b. tension pneumothorax
  - c. hemorrhage from site or excessive drainage (in excess of 1L per hour) in drainage bottle
2. Monitor for:
  - a. Bedside ultrasound of thorax (by chest physician) daily with curvelinear probe (ultrasound Mindray, model Z5) by measuring the maximum distances between the parietal and visceral pleural.
  - b. Serial chest x-ray (baseline x-ray, day 7 post t-PA/DNase and pleural irrigation)
  - c. Serum CRP level (baseline, day 7 post t-PA/DNase and pleural irrigation)
  - d. FBC (baseline, day 1- 3, day 7 post t-PA/DNase and pleural irrigation). Drop of

hemoglobin by less than 10% from baseline is acceptable.

- e. Systemic bleeding/ Pleural bleeding
  - f. Drainage of pleural effusion daily
3. Stop the t-PA & DNase if there is significant drop of haemoglobin (>10% drop Hb) with clinical signs of shock or significant haemorrhagic fluids drained. Consider CTA and blood transfusion in those cases

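### The plan names an independent-samples test, the Wilcoxon rank-sum, for within-group comparisons, although baseline and day-7 opacity, CRP and WBC come from the same patients.

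*Combined protocol and SAP*

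**What the plan says.** The Statistical Analysis section (the second section numbered 3.7) gives three relevant rules. For normal data: "For normally distributed data, parametric test with Student's t-test will be used". For non-normal data: "For non-normally distributed data, the Mann-Whitney test will be used or equivalent nonparametric tests". The next sentence reads: "Within groups, the Wilcoxon rank sum test will be used". No signed-rank test, paired t-test or other paired method is named anywhere in the document.

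The outcomes with a before and an after value are set out elsewhere:

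- Section 2.3 has the objective "To determine the change on inflammatory markers (WBC/CRP) from day 1 (randomization) to day 7" and a parallel one for radiographic opacity.
- Section 3.6, under Medication Regimen, describes the opacity outcome as "change in the area of pleural opacity in chest x-ray (day 7 post t-PA/DNase compared to baseline").
- The monitoring tables in Section 3.6 schedule chest X-ray and CRP at Day 0 and Day 7, and WBC at Days 0 to 3 and Day 7, in both arms.
- Appendix 1 repeats the schedule: "Serial chest x-ray (baseline x-ray, day 7 post t-PA/DNase and pleural irrigation") and "Serum CRP level (baseline, day 7 post t-PA/DNase and pleural irrigation").

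**The concern.** The rank-sum test compares two separate sets of subjects. Applied to one arm's baseline and day-7 values, it treats 39 patients measured twice as 78 unrelated patients. The between-patient spread that pairing would remove stays in the comparison, and the reference distribution no longer fits the data.

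At stake is any before-after p-value reported within an arm for opacity, CRP or WBC. With positive correlation, the usual expectation for two readings on the same patient a week apart, the test rejects too rarely. It does not push false positives above 5%, but it can hide a moderate real change.

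**Working it through.** **Inputs.** Section 3.3 gives 39 patients per arm, which sets the number of pairs. That figure reproduces from the section's own inputs: failure rates 0.15 and 0.32, power 0.8, the printed type I error of 0.5, two-sided, continuity-corrected.

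- Uncorrected: n = [0.6745·√(2·0.235·0.765) + 0.8416·√(0.15·0.85 + 0.32·0.68)]² / 0.17² = 27.96.
- Corrected: (27.96/4)·[1 + √(1 + 4/(27.96·0.17))]² = 38.8, so 39.

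The printed 0.5 is a separate matter; here 39 is only the number of pairs. The Statistical Analysis section sets significance at 0.05; I take it as two-sided, which is not stated. The documents give no within-patient correlation and no SD, so correlations of 0.3, 0.5 and 0.7 and shifts of 0.3, 0.5 and 1 SD are assumptions. The simulations use bivariate normal pairs with equal SDs unless noted.

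**Type I error.** On paired data the null variance of the rank-sum statistic is about (1 − ρs) times the value the test assumes, where ρs = (6/π)·arcsin(ρ/2) is the Spearman correlation. The true two-sided level is therefore about 2·P(Z > 1.96/√(1 − ρs)).

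| ρ | ρs | 1.96/√(1 − ρs) | Level, formula | Level, simulation (200,000 runs) |
|---|---|---|---|---|
| 0.3 | 0.288 | 2.32 | 2.0% | 2.1% |
| 0.5 | 0.483 | 2.72 | 0.6% | 0.7% |
| 0.7 | 0.683 | 3.48 | 0.05% | 0.09% |

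The signed-rank test held 4.7% to 5.1% throughout.

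**Power, rank-sum vs signed-rank (20,000 runs).**

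| Shift | ρ = 0.3 | ρ = 0.5 | ρ = 0.7 |
|---|---|---|---|
| 0.3 SD | 0.21 vs 0.33 | 0.17 vs 0.43 | 0.13 vs 0.63 |
| 0.5 SD | 0.57 vs 0.71 | 0.59 vs 0.84 | 0.61 vs 0.97 |
| 1 SD | above 0.99 for both | above 0.99 for both | above 0.99 for both |

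A second simulation (10,000 runs) gave 0.58 vs 0.71, 0.59 vs 0.84 and 0.62 vs 0.97 in the 0.5 SD row. At ρ = 0.5 and a 0.5 SD shift the median p-value was 0.034 for the rank-sum and 0.005 for the signed-rank test.

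**Hand check with means, ρ = 0.5.** Treated as independent, the standard error of the change is √(2/39) = 0.226 SD; paired, it is √(2·0.5/39) = 0.160 SD. A 0.5 SD shift is then 2.2 standard errors instead of 3.1, the same direction and order of loss.

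**Where the result changes.** At zero correlation the rank-sum level was 4.7%, so little is wrong. At ρ = −0.3 it was 8.1% (formula 8.4%), so the error is not conservative in every case.

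**The case against.** The strongest reply is that this is a slip for signed-rank. Mann-Whitney has just been named, and a separately named Wilcoxon test for use within groups suggests a paired test was meant. That is likely, but it does not settle the matter. An analyst who follows the text gets invalid p-values, and one who silently uses the paired test departs from the plan.

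Four further points limit the finding:

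- The plan does not say which outcomes get a within-group test. Opacity, CRP and WBC are my reading, because Section 2.3 defines them as changes to day 7. Haemoglobin, ultrasound and daily net volume are also repeated.
- The error is conservative under positive correlation, and large changes survive it. At a 0.8 SD shift, power is 0.956 vs 0.981, 0.973 vs 0.997 and 0.992 vs 1.000 at correlations 0.3, 0.5 and 0.7.
- The power figures depend on the assumed distribution. With lognormal data (log-SD 1, shift 0.5 log-SD, correlation 0.5) they are 0.59 vs 0.78, not 0.59 vs 0.84. The loss is smaller but still clear.
- The research question in Section 2.1 is about the difference between arms, and a within-arm p-value does not answer it.

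All four bear on how much the error matters. None makes the named test suitable for paired data.

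**Conclusion.** The concern holds. The plan assigns an independent-samples test to data that are paired by its own schedule, and nothing elsewhere corrects it. At 39 pairs and plausible positive correlations, the actual level falls from 5% to between about 2% and 0.1%. Power for a 0.5 SD change drops by 0.14 to 0.36; for a 1 SD change the loss is negligible. These sizes rest on assumed correlations, shifts and normality.

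The effect is confined to within-arm tests. The primary drained-volume outcome and all five hypotheses in Section 2.4 are comparisons between arms. For opacity, CRP and WBC, an unadjusted t-test or Mann-Whitney test between arms on the changes defined in Section 2.3 is valid.

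**What to change.** Replace the rank-sum test in that sentence with the Wilcoxon signed-rank test, or the paired t-test if the within-patient differences are normal. Name the outcomes it covers: opacity, CRP and WBC, baseline to day 7, plus any other repeated measure to be tested within an arm. Also state which reading is the baseline, since Section 2.3 counts from day 1 while the monitoring tables take CRP and X-ray at Day 0. This costs a change of wording and no new data.

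Optional, and not a correction of an error: prespecify ANCOVA for the between-arm comparison of day-7 opacity, CRP and WBC, each adjusted for its own baseline (transformed or rank-based if skewed), and report the adjusted difference with its 95% CI where the scale allows. The residual variances are 1 for the day-7 value, 2(1 − ρ) for the change and 1 − ρ² for ANCOVA. With 39 per arm and a fixed illustrative effect of 0.643 SD, chosen so that the day-7 test has power 0.80, power is:

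| ρ | Day-7 value | Change | ANCOVA |
|---|---|---|---|
| 0.3 | 0.80 | 0.66 | 0.84 |
| 0.5 | 0.80 | 0.80 | 0.90 |
| 0.7 | 0.80 | 0.95 | 0.98 |

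The baselines are already collected, so this too is only wording. Adjusting the primary volume for baseline opacity is possible, but the gain is small if their unknown correlation is low: power goes from 0.80 to 0.804, 0.816 and 0.836 at correlations of 0.1, 0.2 and 0.3. A log scale would not suit that outcome. Section 3.6 says "The volume drained measured after subtracting the amount of volume administered as per protocol", so net volume can be zero or negative.

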## 2.4 Study Hypothesis

1. Subjects in the IPFT has more volume of pleural fluid drainage compared with pleural irrigation group
2. Subjects in the IPFT has greater reduction of inflammatory parameters compared with pleural irrigation group
3. Subjects in the IPFT has shorter length of hospital stay compared with pleural irrigation group
4. Subjects in the IPFT has less surgical referral rate compared pleural irrigation group
5. There is no difference of mortality rate between both groups

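### Section 3.7 adds significance tests of change within each arm, which could be taken to answer the opacity and CRP/WBC objectives although they say nothing about IPFT versus irrigation

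*Combined protocol and SAP*

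**What the plan says.** Section 3.7 Statistical Analysis names tests by type of data, not by outcome. For numerical data it says "For normally distributed data, parametric test with Student's t-test will be used" and "For non-normally distributed data, the Mann-Whitney test will be used or equivalent nonparametric tests". Chi-square and Fisher's exact tests cover qualitative data. It then adds "Within groups, the Wilcoxon rank sum test will be used". The significance level is 0.05, and "in the case of multiple comparisons it will be adjusted with a Bonferonni correction". The section does not define the family of comparisons, call the within-group results descriptive, or say that the between-arm tests decide the hypotheses.

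The research question in Section 2.1 and all five hypotheses in Section 2.4 compare the two arms. For the markers, the hypothesis is "Subjects in the IPFT has greater reduction of inflammatory parameters compared with pleural irrigation group". The matching objective in Section 2.3 has no comparator: "To determine the change on inflammatory markers (WBC/CRP) from day 1 (randomization) to day 7". The opacity objective in Section 2.3 is also a change over time without a comparator, and no hypothesis in Section 2.4 concerns opacity. Section 3.6 defines the opacity outcome as a day 7 value against baseline and mentions only t-PA/DNase there. Appendix 1 schedules the day 7 film for both treatments.

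**The concern.** A within-arm test asks whether a marker or the opacity changed over the week. In this trial every patient has a chest drain, and both arms receive standard care (Section 3.6). Improvement is therefore possible in either arm whatever the intrapleural treatment adds. A small within-arm p-value cannot separate the effect of IPFT or irrigation from the effect of drainage and standard care, and it cannot compare the two.

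Two wrong readings are left open. If only one arm reaches p<0.05, that arm may be called better although the arms do not differ. If both do, each treatment may be said to work although there is no untreated comparison. What is at stake is the conclusion on three secondary outcomes: opacity, CRP and WBC. Opacity is the most exposed, because neither its objective nor any hypothesis asks for a comparison.

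**Working it through.** **Inputs from the documents.** Two arms of 39 (Section 3.3) and a significance level of 0.05 (Section 3.7). Sidedness is not stated, so two-sided is assumed. The documents give no SD for change in opacity, CRP or WBC, so the size of change in SD units is an assumption and is varied.

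**The plan's own figure.** The plan gives no number for this point. The 39 per arm used here does reproduce from Section 3.3 as printed (rates 0.15 and 0.32, power 0.8, type I error 0.5, two-sided):

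- Uncorrected: n = [0.6745 × √(2 × 0.235 × 0.765) + 0.8416 × √(0.15 × 0.85 + 0.32 × 0.68)]² / 0.17² = 27.96.
- With continuity correction: (27.96 / 4) × [1 + √(1 + 4 / (27.96 × 0.17))]² = 38.8, which rounds up to 39.

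The type I error of 0.5 is a separate matter. Here 39 is only the planned arm size.

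**Formula.** Let the true change be equal in both arms and let each within-arm test have power p. The arms are independent, so

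P(exactly one arm below 0.05) = p(1-p) + (1-p)p = 2p(1-p).

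- p = 0.50: 2 × 0.50 × 0.50 = 50%, the maximum (25% for each arm alone)
- p = 0.80: 2 × 0.80 × 0.20 = 32%
- p = 0.90: 2 × 0.90 × 0.10 = 18%
- p = 0.95: 2 × 0.95 × 0.05 = 9.5%

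**Simulation.** 39 per arm, normal change scores with the same mean in both arms, 4,000 runs per row. The within-arm test is a paired signed-rank test; the between-arm test is Mann-Whitney on the change.

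| True change in both arms (SD of change) | Within-arm power | Exactly one arm p<0.05 | Between-arm test p<0.05 |
|---|---|---|---|
| 0 | 5.5% | 9% | 4.5% |
| 0.2 | 21% | 33% | 4.5% |
| 0.3 | 44% | 49% | 4.3% |
| 0.45 | 77% | 35% | 4.8% |
| 0.6 | 95% | 10% | 4.2% |
| 0.8 | 99.8% | 0.5% | 4.6% |

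The formula agrees: at 0.45 SD, 2 × 0.773 × 0.227 = 35%. In the last two rows almost every trial has both arms below 0.05, so the second misreading replaces the first.

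**Where this trial might lie.** The only spread figures in the documents are for CT pleural volume in the irrigation trial cited in Section 3.3. Taking SD = IQR / 1.349:

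- Irrigation: SD = (43.7 - 19.6) / 1.349 = 17.9; change = 32.3 / 17.9 = 1.8 SD.
- Standard care: SD = (28 + 5.5) / 1.349 = 24.8; change = 15.3 / 24.8 = 0.6 SD.

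At 1.8 SD the discordance is about 0. At 0.62 SD simulated power was 0.96, so it is 2 × 0.96 × 0.04 = 8%. These figures concern another outcome in another trial, and CRP or WBC changes could be smaller in SD units.

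**The named test.** The rank sum test is the Mann-Whitney test, for independent samples, whereas baseline and day 7 values in one arm are paired. In a simulation with n = 39 and 3,000 runs, at assumed baseline to day 7 correlations of 0.3, 0.5 and 0.7, rank sum on paired data had a type I error of 2.3%, 0.8% and 0.03%. Its power for a shift of 0.5 SD of the measurement was 56%, 58% and 59%, against 71%, 83% and 96% for signed-rank. Correcting the name would repair this, but would not make the test a comparison of treatments.

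**The case against.** The strongest reply is that the comparison is already planned. Mann-Whitney is a two-group test, and the contrast with the phrase on within-group testing shows that the sentences before it are meant for the arms. A reader might infer from the within-group line that the hypotheses have no between-arm test; Section 3.7 does not support that. A reader might also infer that the investigators intend to compare one arm's p-value with the other's. No passage says so, and Section 2.4 puts the marker question as a comparison. Both replies stand. The fault is silence about the role of the within-arm tests, not a planned wrong inference.

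It is also fair to say that figures of 32-50% come from modest assumed changes. If markers and opacity fall steeply, as drainage and antibiotics might produce, both arms will reach p<0.05 and discordance nearly vanishes. That stands too, so those figures are not an expected risk. It does not rescue the within-arm tests, because two small p-values still say nothing about which treatment is better.

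Finally, the scope is narrow. Drainage volume has its own between-arm hypothesis, "Subjects in the IPFT has more volume of pleural fluid drainage compared with pleural irrigation group", and stay, surgery and mortality are not before-after changes. What remains is that the plan assigns no test to opacity, CRP or WBC, and that the objectives for them read as single-group questions.

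**Conclusion.** The point holds as a limited one that should be corrected. Section 3.7 includes a within-arm significance test that answers no stated hypothesis, and nothing prevents its result from being read as a treatment difference for opacity, CRP or WBC. With equal true change in both arms and 39 per arm, reading one-arm-only significance as a difference would be wrong in about 0-50% of trials, against about 5% for a direct between-arm test. The position in that range depends on the standardised change, which the documents do not give. The calculation further assumes normal change scores, independent arms, a paired test and two-sided 0.05. The primary outcome, length of stay, surgery and mortality are not affected.

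**What to change.** 1. In Section 3.7, remove the within-group significance test. Report change from baseline to day 7 in opacity, CRP and WBC for each arm descriptively, without p-values.
2. In Section 2.3, word the opacity and CRP/WBC objectives as comparisons of the change between IPFT and irrigation.
3. State in Section 3.7 that conclusions on these outcomes rest on the between-arm difference in change with its 95% CI, preferably adjusted for the baseline value, and name the test for each outcome.
4. If a within-arm test is kept, label it descriptive and make it a paired signed-rank test. Say also that it lies outside the Bonferroni family.

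This costs a few sentences and no patients, visits or data. The only loss is a set of within-arm p-values that answer no stated hypothesis.
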